3. PATIENT SELECTION

3.1 Inclusion Criteria

For both Cohort A and B patients:

3.1.1 Patients must have histologically or cytologically confirmed thyroid carcinoma of follicular origin (including papillary, follicular, or poorly differentiated subtypes and their respective variants). Confirmation of thyroid carcinoma will be done at MSK.

3.1.2 Patients must have measurable disease, defined as at least one lesion that can be accurately measured in at least one dimension (longest diameter to be recorded for non-nodal lesions and short axis for nodal lesions) as ≥ 20 mm with conventional techniques or as ≥ 10 mm with spiral CT scan, MRI, or calipers by clinical exam. See [Section 11](#) for the evaluation of measurable disease. Tumors in previously irradiated fields may be considered measurable if there is evidence of tumor progression after radiation treatment.

3.1.3 RAI-refractory disease on structural imaging, defined as any one of the following:

- a) A metastatic lesion that is not radioiodine-avid on a diagnostic radioiodine scan performed prior to enrollment in the current study, or
- b) A radioiodine-avid metastatic lesion which remained stable in size or progressed despite radioiodine treatment 6 months or more prior to entry in the study. There are no size limitations for the index lesion used to satisfy this entry criterion.
- c) The presence of at least one fluorodeoxyglucose (FDG) avid lesion.

3.1.4 No recent treatment for thyroid cancer as defined as:

- a) No prior RAI therapy is allowed < 6 months prior to initiation of therapy on this protocol. A diagnostic study using < 10 mCi of RAI is not considered RAI therapy.
- b) No external beam radiation therapy < 4 weeks prior to initiation of therapy on this protocol. (Previous treatment with radiation for any indication is allowed if

the investigator judges that the previous radiation does not significantly compromise patient safety on this protocol.)

- c) No chemotherapy or targeted therapy (e.g., tyrosine kinase inhibitor) is allowed < 4 weeks prior to the initiation of therapy on this protocol.

3.1.5 Age \geq 18 years. Because no dosing or adverse event data are currently available on the use of trametinib alone or in combination with RAI in patients < 18 years of age, children are excluded from this study.

3.1.6 ECOG performance status \leq 2 (Karnofsky \geq 60%, see [Appendix A](#)).

3.1.7 Life expectancy of greater than 3 months.

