11.1.2 Disease Parameters

Measurable disease. Measurable lesions are defined as those that can be accurately measured in at least one dimension (longest diameter to be recorded) as ≥ 20 mm by chest x-ray or as ≥ 10 mm with CT scan, MRI, or calipers by clinical exam. All tumor

measurements must be recorded in millimeters (or decimal fractions of centimeters).

Note: Tumor lesions that are situated in a previously irradiated area might or might not be considered measurable. *If the investigator thinks it appropriate to include them, the conditions under which such lesions should be considered must be defined in the protocol.*

Malignant lymph nodes. To be considered pathologically enlarged and measurable, a lymph node must be ≥ 15 mm in short axis when assessed by CT scan (CT scan slice thickness recommended to be no greater than 5 mm). At baseline and in follow-up, only the short axis will be measured and followed.

Non-measurable disease. All other lesions (or sites of disease), including small lesions (longest diameter < 10 mm or pathological lymph nodes with ≥ 10 to < 15 mm short axis), are considered non-measurable disease. Bone lesions, leptomeningeal disease, ascites, pleural/pericardial effusions, lymphangitis cutis/pulmonitis, inflammatory breast disease, and abdominal masses (not followed by CT or MRI), are considered as non-measurable.

Note: Cystic lesions that meet the criteria for radiographically defined simple cysts should not be considered as malignant lesions (neither measurable nor non-measurable) since they are, by definition, simple cysts.

‘Cystic lesions’ thought to represent cystic metastases can be considered as measurable lesions, if they meet the definition of measurability described above. However, if non-cystic lesions are present in the same patient, these are preferred for selection as target lesions.

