Target lesions. All measurable lesions up to a maximum of 2 lesions per organ and 5 lesions in total, representative of all involved organs, should be identified as **target lesions** and recorded and measured at baseline. Target lesions should be selected on the basis of their size (lesions with the longest diameter), be representative of all involved organs, but in addition should be those that lend themselves to reproducible repeated measurements. It may be the case that, on occasion, the largest lesion does not lend itself to reproducible measurement in which circumstance the next largest lesion which can be measured reproducibly should be selected. A sum of the diameters (longest for non-nodal lesions, short axis for nodal lesions) for all target lesions will be calculated and reported as the baseline sum diameters. If lymph nodes are to be included in the sum, then only the short axis is added into the sum. The baseline sum diameters will be used as reference to further characterize any objective tumor regression in the measurable dimension of the disease.

Non-target lesions. All other lesions (or sites of disease) including any measurable lesions over and above the 5 target lesions should be identified as **non-target lesions** and should also be recorded at baseline. Measurements of these lesions are not required, but the presence, absence, or in rare cases unequivocal progression of each should be noted throughout follow-up.

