11.1.4.3 Evaluation of Best Overall Response

The best overall response is the best response recorded from the start of the treatment until disease progression/recurrence (taking as reference for progressive disease the smallest measurements recorded since the treatment started). The patient's best response assignment will depend on the achievement of both measurement and confirmation criteria.

For Patients with Measurable Disease (*i.e.*, Target Disease)

Target Lesions	Non-Target Lesions	New Lesions	Overall Response	Best Overall Response when Confirmation is Required*
CR	CR	No	CR	≥ 4 wks. Confirmation**
CR	Non-CR/Non-PD	No	PR	
CR	Not evaluated	No	PR	
PR	Non-CR/Non-PD/not evaluated	No	PR	≥ 4 wks. Confirmation**
SD	Non-CR/Non-PD/not evaluated	No	SD	Documented at least once ≥ 4 wks. from baseline**
PD	Any	Yes or No	PD	no prior SD, PR or CR

Any	PD***	Yes or No	PD	
Any	Any	Yes	PD	

 • See RECIST 1.1 manuscript for further details on what is evidence of a new lesion. 				

** Only for non-randomized trials with response as primary endpoint.
				

*** In exceptional circumstances, unequivocal progression in non-target lesions may be accepted as disease progression.
				

Note: Patients with a global deterioration of health status requiring discontinuation of treatment without objective evidence of disease progression at that time should be reported as “symptomatic deterioration.” Every effort should be made to document the objective progression even after discontinuation of treatment.
				

For Patients with Non-Measurable Disease (i.e., Non-Target Disease)

Non-Target Lesions	New Lesions	Overall Response
CR	No	CR
Non-CR/non-PD	No	Non-CR/non-PD*
Not all evaluated	No	not evaluated
Unequivocal PD	Yes or No	PD
Any	Yes	PD

 • ‘Non-CR/non-PD’ is preferred over ‘stable disease’ for non-target disease since SD is increasingly used as an endpoint for assessment of efficacy in some trials so to assign this category when no lesions can be measured is not advised 		

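### Sections 3.1.2 and 11.1.2 set different nodal cut-offs (10 mm and 15 mm short axis), so a patient whose only disease is nodes of 10 to <15 mm can enrol with no target lesion and no route to PR

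*Combined protocol and SAP*

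**What the plan says.** **Entry.** Section 3.1.2 requires at least one measurable lesion. It states the dimension as "longest diameter to be recorded for non-nodal lesions and short axis for nodal lesions". It then gives one set of size limits for both kinds of lesion: 20 mm or more with conventional techniques, or at least "10 mm with spiral CT scan, MRI, or calipers by clinical exam". It refers to Section 11 "for the evaluation of measurable disease" but does not itself state a 15 mm limit for nodes.

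**Response.** Section 11.1.2 says that to be measurable "a lymph node must be ≥ 15 mm in short axis when assessed by CT scan". Small lesions, including "pathological lymph nodes with ≥ 10 to < 15 mm short axis), are considered non-measurable disease", fall outside the definition. Target lesions are drawn from "All measurable lesions up to a maximum of 2 lesions per organ and 5 lesions in total". Section 11.1.4.1 defines PR as a fall of at least 30% in the sum of target-lesion diameters. Section 11.1.4.3 has a separate table headed "For Patients with Non-Measurable Disease (i.e., Non-Target Disease"). Its outcomes are CR, non-CR/non-PD, not evaluated and PD; PR is not among them.

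**Caliper rule.** Section 11.1.3 treats superficial lesions, palpable nodes included, as measurable from 10 mm by calipers, while preferring imaging where a lesion can be imaged.

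**Decision rule.** Section 13.1 calls the regimen worthy of further testing in Cohort A if at least 4 of 25 patients respond (CR + PR), or if at least 9 of 25 are alive and progression-free, at 6 months.

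**The concern.** The same term is defined twice, on the same axis, with different numbers. Staff completing the eligibility checklist (Section 4.2) could pass a patient with a single 12 mm node on the words of 3.1.2, and the radiologist applying 11.1.2 would then find nothing to select as a target.

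Other entry criteria do not reliably screen this patient out. The refractory-disease criterion in 3.1.3(b) sets no size limit for its lesion, and the dosimetry index lesion in 5.1.4 needs only 5 mm. The denominator rules do not remove the patient either. Section 13.1 counts everyone treated through the second ¹²⁴I PET, and 13.5.2 counts all eligible patients who took one dose. Section 11.1.1 refers evaluability for response to Section 13, which has no rule for a patient without a target lesion.

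At stake is a co-primary endpoint with a fixed cut-off of 4 in a cohort of 25, where each patient with a restricted route to response costs some power. The 6-month response endpoint in Cohort B and best response in Cohort C use the same criteria. Cohort B's own primary endpoint is dosimetric and is not touched.

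**Working it through.** **1. The path of one patient.** Take a patient whose only disease is one node of 12 mm short axis on CT, not assessable by calipers.

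| Step | Rule | Result |
|---|---|---|
| Entry, 3.1.2 | short axis ≥10 mm on spiral CT | measurable, eligible |
| Baseline, 11.1.2 | node ≥15 mm on CT | non-measurable |
| Target selection, 11.1.2 | measurable lesions only | no target lesion |
| PR, 11.1.4.1 | ≥30% fall in target sum | not defined |
| Response table, 11.1.4.3 | non-target disease | CR, non-CR/non-PD, not evaluated or PD |
| Denominator, 13.1 and 13.5.2 | no exclusion | counted |

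**2. Reproducing the plan's figures.** Inputs from Section 13.1: n = 25, success at 4 or more responses, true ORR 5% against 25%.

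Power = 1 − Σ(x = 0 to 3) C(25, x) 0.25^x 0.75^(25−x) = 1 − (0.0008 + 0.0063 + 0.0251 + 0.0641) = 0.904. The plan states 90%, so it reproduces. The same sum at 5% gives a type I error of 0.034 (plan: 0.04).

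For the progression-free rule (9 or more of 25, 20% against 50%), power is 0.946 (plan: 94%) and type I error 0.047 (plan: 0.05).

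**3. Effect on ORR power.** Let k be the number of Cohort A patients with no target lesion. The documents do not give k, so it is an assumption. The other 25 − k respond at the design value of 25% and the cut-off stays at 4.

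- No response possible in the k patients: X ~ Bin(25 − k, 0.25).
- A 5% chance of CR in each: X = Bin(25 − k, 0.25) + Bin(k, 0.05).

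The 5% is also an assumption. Power is P(X ≥ 4).

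| k | Cohort ORR if the k cannot respond | Power, none can respond | Power, 5% CR each |
|---|---|---|---|
| 0 | 0.25 | 0.904 | 0.904 |
| 1 | 0.24 | 0.885 | 0.889 |
| 2 | 0.23 | 0.863 | 0.872 |
| 3 | 0.22 | 0.838 | 0.853 |
| 5 | 0.20 | 0.775 | 0.807 |

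The second column is 0.25 × (25 − k)/25.

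**4. Effect on the overall decision.** Either co-primary suffices. Assume independence, as Section 13.1 does, and leave the progression-free endpoint unaffected at 0.946. Then P(at least one met) = 1 − (1 − ORR power)(1 − 0.946), computed with unrounded values and no response in the k patients:

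- k = 0: 1 − 0.0962 × 0.0539 = 0.995
- k = 2: 1 − 0.1370 × 0.0539 = 0.993
- k = 3: 1 − 0.1624 × 0.0539 = 0.991
- k = 5: 1 − 0.2252 × 0.0539 = 0.988

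**5. Type I error.** At a true ORR of 5% in the remaining patients and none in the k, it falls from 0.034 to 0.026 (k = 2), 0.022 (k = 3) and 0.016 (k = 5). The error is in the conservative direction.

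**The case against.** The best defence is that Section 3.1.2 sends the reader to Section 11, where the node-specific rule sits, and that a specific rule should govern a general one. On this view the parenthesis in 3.1.2 only says which dimension to record. That may well be the intent. But 3.1.2 names the short axis of nodes and gives 10 mm in the same sentence, and the pointer comes only after that definition. A reader who follows the entry criterion as written is not in error, so the conflict stands.

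Three further points do stand, and they limit the finding.

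- **Calipers.** Under 11.1.3 a palpable node of 10 mm or more may be measurable, and so a target. This narrows the affected group. Because the same section prefers imaging, it does not close the gap, and it leaves two nodal limits within Section 11.
- **CR remains open and counts toward the 4.** The size part need not be harder than PR: a 30% fall takes a 14 mm node to 14 × 0.7 = 9.8 mm, below the 10 mm required. What is harder is that every node must be below 10 mm and any raised tumor marker must normalize (11.1.4.2). Section 2.4 describes thyroglobulin as such a marker. The zero-response column is therefore a worst case.
- **Either co-primary suffices**, so the overall decision barely moves.

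A reader might infer that node-only patients in general are affected. They are not: any node of 15 mm or more is a target lesion. A reader might also infer that the progression-free co-primary cannot be scored for these patients. It can, through new lesions and progression of non-target disease.

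**Conclusion.** This is an internal inconsistency in the definition of measurable disease, and it should be corrected. It affects only patients whose sole disease is nodes of 10 to <15 mm short axis and who do not qualify by calipers. For them PR is unavailable, CR is possible, and the denominator still includes them.

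The size is illustrative because k is unknown. Each such patient costs roughly 2 to 3 points of Cohort A ORR power if none can respond, and somewhat less if CR is allowed for. Five patients would be 20% of the cohort, and nothing in the documents supports a number that high, or shows that any such patient was enrolled.

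It would be tempting to conclude that the trial's go/no-go decision is compromised. The documents do not support that. The chance of meeting at least one co-primary goes from 0.995 to 0.988 even at k = 5, given independence and an unaffected progression endpoint, and the ORR type I error falls. The harm is to the clarity and power of the ORR result, not to protection against a false positive.

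**What to change.** - **Reconcile the text.** Make 3.1.2, 11.1.2 and the caliper rule for palpable nodes in 11.1.3 state one nodal definition that governs both entry and target-lesion selection, with 3.1.2 aligned to the Section 11 nodal rule. Say explicitly whether a palpable node of 10 to <15 mm measured by calipers may be a target lesion.
- **Patients already enrolled.** From the baseline measurements, list any patient with no RECIST 1.1 target lesion, by cohort. Keep the primary ORR on the planned denominator and the cut-off at 4 of 25. Add a sensitivity ORR without the listed patients, labelled as such.

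The cost is about one sentence in eligibility, a clarification in 11.1.3, one listing and one extra estimate. The downside is that a few patients with only 10 to <15 mm nodes may become ineligible. If accrual is complete, the listing and the sensitivity estimate are still worth having.

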3.2 Exclusion Criteria

3.2.1 History of another malignancy.

Exception: Patients who have been disease-free for 3 years, patients with a history of completely resected non-melanoma skin cancer, and/or patients with indolent secondary malignancies, are eligible. MSK can consult the CTEP Medical Monitor if unsure whether second malignancies meet the requirements specified above.

3.2.2 History of interstitial lung disease or pneumonitis.

3.2.3 Use of other investigational drugs within 28 days (or five half-lives, whichever is shorter; with a minimum of 14 days from the last dose) preceding the first dose of trametinib and during the study.

3.2.4 Symptomatic or untreated leptomeningeal or brain metastases or spinal cord compression.

3.2.5 Have a known immediate or delayed hypersensitivity reaction or idiosyncrasy to drugs chemically related to trametinib, or excipients or to dimethyl sulfoxide (DMSO) or to thyrotropin alpha (Thyrogen).

3.2.6 Current use of a prohibited medication. The following medications or non-drug therapies are prohibited:

- Other anti-cancer therapy while on study. (Note: Megestrol [Megace] if used as an appetite stimulant is allowed. TSH suppressive therapy is also allowed. Palliative radiation therapy to non-target lesions is also allowed.).
- Concurrent treatment with bisphosphonates is permitted. Prophylactic use of bisphosphonates in patients without bone disease is not permitted, except for the treatment of osteoporosis.
- Because the composition, PK, and metabolism of many herbal supplements are unknown, the concurrent use of all herbal supplements is prohibited during the study (including, but not limited to, St. John's wort, kava, ephedra [ma huang], gingko biloba, dehydroepiandrosterone [DHEA], yohimbe, saw palmetto, or ginseng).

3.2.7 Patients with the following ophthalmological findings/conditions:

- Intraocular pressure >21 mmHg, or uncontrolled glaucoma (irrespective of intraocular pressure)
- Current or past history of central serious retinopathy or retinal vein occlusion

3.2.8 History or evidence of cardiovascular risk including any of the following:

- LVEF $<$ LLN.
- A QT interval corrected for heart rate using the Bazett's formula QTcB ≥ 480 msec.
- History or evidence of current clinically significant uncontrolled arrhythmias (Exception: patients with controlled atrial fibrillation for >30 days prior to randomization are eligible).
- History of acute coronary syndromes (including myocardial infarction and unstable angina), coronary angioplasty, or stenting within 6 months prior to randomization.
- History or evidence of current \geq Class II congestive heart failure as defined by the New York Heart Association (NYHA) functional classification system.
- Treatment-refractory hypertension defined as a blood pressure of systolic >140

mmHg and/or diastolic >90 mmHg which cannot be controlled by anti-hypertensive therapy.

- Patients with intra-cardiac defibrillators.
- Known cardiac metastases.

3.2.9 Known Human Immunodeficiency Virus (HIV), Hepatitis B Virus (HBV), or Hepatitis C Virus (HCV) infection (with the exception of chronic or cleared HBV and HCV infection, which will be allowed). Patients with Human Immunodeficiency Virus (HIV) are not eligible if on anti-retroviral medications,

3.2.10 Uncontrolled intercurrent illness including, but not limited to, ongoing or active infection, symptomatic congestive heart failure, unstable angina pectoris, cardiac arrhythmia, or psychiatric illness/social situations that would limit compliance with study requirements.

3.2.11 Animal reproductive studies have not been conducted with trametinib. Therefore, the study drug must not be administered to pregnant women or nursing mothers. These potential risks may also apply to RAI and Thyrogen.

3.2.12 HIV-positive patients on combination antiretroviral therapy are ineligible because of the potential for pharmacokinetic interactions with trametinib. In addition, these patients are at increased risk of lethal infections when treated with marrow-suppressive therapy.

3.2.13 Patients unable to follow a low iodine diet or requiring medication with high content in iodide (amiodarone).

3.2.14 Patients who received iodinated intravenous contrast as part of a radiographic procedure within 3 months of study registration. Those that have had iodinated intravenous contrast within this time frame may still be eligible if an urinary iodine analysis reveals that the excess iodine has been cleared after the last intravenous contrast administration.

3.3 Inclusion of Women and Minorities

Both men and women of all races and ethnic groups are eligible for this trial. (NOTE: The letter designations below do not refer to study cohort designations.)

Accrual Targets						
Ethnic Category	Sex/Gender					
	Females		Males	Total		
Hispanic or Latino	4	+	2	= 6		
Not Hispanic or Latino	16	+	13	= 29		
Ethnic Category: Total of all subjects	20	(A1)	15	(B1) = 35 (C1)		
Racial Category						
American Indian or Alaskan Native	0	+	0	= 0		
Asian	2	+	1	= 3		
Black or African American	3	+	2	= 5		
Native Hawaiian or other Pacific Islander	0	+	0	= 0		
White	15	+	12	= 27		
Racial Category: Total of all subjects	20	(A2)	15	(B2) = 35 (C2)		
	(A1 = A2)		(B1 = B2)			

4. REGISTRATION PROCEDURES

4.1 Investigator and Research Associate Registration with CTEP

Food and Drug Administration (FDA) regulations and National Cancer Institute (NCI) policy require all individuals contributing to NCI-sponsored trials to register and to renew their registration annually. To register, all individuals must obtain a Cancer Therapy Evaluation Program (CTEP) Identity and Access Management (IAM) account (<https://ctepcore.nci.nih.gov/iam>). In addition, persons with a registration type of Investigator (IVR), Non-Physician Investigator (NPIVR), or Associate Plus (AP) (i.e., clinical site staff requiring write access to OPEN or RAVE or acting as a primary site contact) must complete their annual registration using CTEP's web-based Registration and Credential Repository (RCR) (<https://ctepcore.nci.nih.gov/rrc>). Documentation requirements per registration type are outlined in the table below.

Documentation Required	IVR	NPIVR	AP	A
FDA Form 1572	✓	✓		
Financial Disclosure Form	✓	✓	✓	
NCI Biosketch (education, training, employment, license, and certification)	✓	✓	✓	
HSP/GCP training	✓	✓	✓	
Agent Shipment Form (if applicable)	✓			
CV (optional)	✓	✓	✓	

An active CTEP-IAM user account and appropriate RCR registration is required to access all CTEP and CTSU (Cancer Trials Support Unit) websites and applications. In addition, IVRs and NPIVRs must list all clinical practice sites and IRBs covering their practice sites on the FDA Form 1572 in RCR to allow the following:

- Added to a site roster
- Assigned the treating, credit, consenting, or drug shipment (IVR only) tasks in OPEN
- Act as the site-protocol PI on the IRB approval
- Assigned the Clinical Investigator (CI) role on the Delegation of Tasks Log (DTL).

Additional information can be found on the CTEP website at <https://ctep.cancer.gov/investigatorResources/default.htm>. For questions, please contact the RCR *Help Desk* by email at [contact]

